#### 7.1.3.2 Procedures for Reviewing Early Termination/Discontinuation Categories

- In the weekly Tonix-CRO clinical study team meeting, all new ETs are reviewed, and the CRO Clinical Manager (CM) is instructed by the Sponsor when follow-up is needed on specific patients
- The sponsor instructs our CRO CM to contact each site for any ET due to Investigator Decision, WOC, Patient Non-Compliance, and Other. The CM has a templated email for this purpose, specifically to ensure that the PI has carefully evaluated the ET reason, including an evaluation of AE and efficacy data to ensure the ET reason is reasonable. Within the email the participant's CAPS-5 and PGIC efficacy data is included as well as a listing of all the participant's AEs to assist their review.
- The Sponsor conducts a periodic review of the discontinuation listings to ensure any necessary change of category has been made and that the specific reason supporting the categorization has been documented.

## 7.2 Efficacy Assessments

There is one primary efficacy endpoint and three key secondary endpoints intended for the labeling. Other secondary and exploratory efficacy endpoints are tested to better understand the potential clinical benefit of TNX-102 SL on PTSD participants.

### 7.2.1 Primary Efficacy

### 7.2.2 Clinician-Administered PTSD Scale for DSM-5 (CAPS-5)

The primary efficacy endpoint is the change from baseline in total CAPS-5 score at Week 12 (Visit 6).

The CAPS-5 is an updated and validated version of a semi-structured interview that has been designed to assess the essential features of PTSD as defined by the DSM-5 ([Weathers et al, 2013](#)). The CAPS-5 affords the clinician flexibility to inquire about symptoms and diagnostic status over different time frames, such as past week, past month, and/or worst month for lifetime. For this study, a “Diagnostic” version of the CAPS-5 (past month recall) will be utilized at the Screening visit to confirm the diagnosis of PTSD and determine eligibility. A “Symptom Severity” version of the CAPS-5 (past week recall) will be completed by the clinician at all other time points (Baseline [Visit 2] and after 4, 8, and 12 weeks of treatment [Visits 4, 5, and 6, respectively]).

The CAPS-5 interview contains the following components

- Life Events Checklist for DSM-5 (LEC-5): Completed by the participant at the Screening Visit (Visit 1 only)
- Criterion A – Assessment Form (CA-AF): this semi-structured interview is based on the Criterion A discussion included in the CAPS-5, but modified (by [name], CAPS-5 lead author, in conjunction with the Sponsor P302 study team) specifically for this study to ensure sufficient review of the traumas outlined on the participant-completed LEC-5 and to capture clear description of the participant’s index/qualifying trauma (Visit 1 only)
- PTSD symptoms, onset/duration, distress/impairment, global rating, and dissociative symptoms:
  - Criterion B: Items 1-5 (Intrusion symptoms)
  - Criterion C: Items 6-7 (Avoidance symptoms)
  - Criterion D: Items 8-14 (Negative alterations in cognitions & mood)
  - Criterion E: Items 15-20 (Arousal and reactivity symptoms)
  - Criterion F: Items 21-22 (Onset and duration of symptoms)
  - Criterion G: Items 23-25 (Distress and impairment due to PTSD)
  - Global ratings: Items 26-27 (Validity, severity)
  - Dissociative symptoms: Items 29 (Depersonalization) and 30 (Derealization)

In addition to the total symptom score (obtained from the sum of Criteria B-E), the CAPS-5 affords the opportunity to examine clusters of symptoms, including Criterion B (intrusion symptoms), Criterion C (persistent avoidance), Criterion D (negative

cognitions and mood), and Criterion E (arousal and reactivity), all of which will be secondary efficacy endpoints.

In the case of CAPS-5 items that are not resolvable at the site level (via query, review of source), the following conventions will be employed for handling of missing CAPS-5 items:

- For  $\leq 2$  missing item scores in Criterion B, D, or E, the average of the other items within the criterion will be used for the missing item;
- For  $< 2$  missing items scores in Criterion C, which only has 2 items, the value of the non-missing items will be used for the missing item;
- For  $> 2$  missing items in Criterion B, D, or E, or  $> 1$  missing item in the Criterion C, the total CAPS-5 score will be considered missing overall.

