##### 7.2.4.4.2 Loss of Diagnosis

Loss of Diagnosis at any time point is defined as Response AND no longer meeting DSM-5 symptom criteria required for diagnosis on the CAPS-5 in any one or more of the four clusters (B, C, D, E).

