## 9.2 Secondary Efficacy Analysis

### 9.2.1 Continuous outcomes

The analyses of continuous secondary endpoints will be analyzed using an MMRM model identical to the primary endpoint, however, there will be no multiple imputation applied. These endpoints will include:

- CGI-S score.
- Change from baseline in SDS total.
- Change from baseline in participants' quality of sleep using the PROMIS Sleep Disturbance scale T-scores.
- CGI-I score
- Change from baseline in the disruption of work/school activities assessed using the SDS.
- Change from baseline in disruption of social life/ leisure activities assessed using the SDS.
- Change from baseline in the disruption of family life/home responsibilities assessed using the SDS.
- Change from baseline in CAPS-5 Arousal and Reactivity (Criterion E).
- Change from baseline in CAPS-5 Intrusion symptoms (Criterion B).
- Change from baseline in CAPS-5 Negative Cognition and Mood (Criterion D).
- Change from baseline in CAPS-5 Persistent Avoidance (Criterion C).
- Change from baseline in CAPS-5 Sleep Disturbance (item E-6).
- Mean PGIC score

- Change from baseline in CAPS-5 Reckless or Self-Destructive Behavior (item E-2).
- Changes from baseline in patient-rated Changes in Sexual Functioning Questionnaire Short-Form (CSFQ-14) in males and in females, analyzed separately
- Change from baseline in MADRS score.

The model will be changed to include the corresponding baseline value of the secondary endpoints instead of baseline CAPS-5. Randomized participants who have a baseline and at least one post-baseline assessment for the endpoint being analyzed will be included in the model. To estimate the difference between the treatment arms in CGI-I and PGIC scores (which do not have baseline assessments), the same method will be used, however, with the observed baseline response and associated interactions removed from the list of covariates. All visits will be included in the analysis. P-values from these comparisons will be considered nominal (conclusions from the sequential testing algorithm will be reported separately).

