### **9.2.2 Categorical outcomes**

Binary data over time will be analyzed using a Cochran Mantel Haenszel (CMH) test stratified by presence of current major depressive episode. Examples include the CGI-I and the PGIC, in which responders are defined as those who score ‘2’ (much improved) or ‘1’ (very much improved) on these 7-point scales. Participants with missing data will be analyzed as though they are non-responders. This will be reported for each visit with the primary time point of interest at Week 12 (with remission spanning data at weeks 8 and 12). Odds ratios for treatment contrasts along with two-sided 95% CIs will also be reported. Two-sided p-values for the test of no difference between the TNX-102 SL and placebo will be provided.

These endpoints will include:

- Proportion of participants with a PGIC score of “much improved” or “very much improved”.
- Proportion of participants with a CGI-I score of “much improved” or “very much improved”.
- Proportion of participants with a CAPS-5 total score of 0 –10 (asymptomatic/few symptoms).

- Proportion of participants with a CAPS-5 total score of 0-22 (asymptomatic or mild PTSD/subthreshold).
- Proportion of participants with Response, defined as a  $\geq$  10-point improvement from baseline in CAPS-5 total score.
- Proportion of participants with Loss of Diagnosis, defined as Response AND no longer meeting DSM-5 symptom criteria in any one or more of the four clusters (B, C, D, E).
- Proportion of participants in Remission, defined as Loss of Diagnosis AND Total CAPS-5 score  $\leq$  10.
- Proportion of participants achieving sustained Remission, defined as Loss of Diagnosis AND Total CAPS-5 score  $\leq$  10 after both 8 weeks AND 12 weeks of treatment.
- Proportion of participants with a  $\geq$ 50% improvement from baseline in CAPS-5 total score.

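### The averaging rule for missing CAPS-5 items is not limited to sums: E-2 and E-6 can be scored from other symptoms, and cluster status in Loss of Diagnosis leans towards not met

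*SAP*

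**What the plan says.** SAP 7.2.2 introduces the rule in general terms: "the following conventions will be employed for handling of missing CAPS-5 items". It applies only to items that query and source review at the site cannot resolve.

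- Criteria B, D and E, up to two items missing: "the average of the other items within the criterion will be used for the missing item".
- Criterion C, one of its two items missing: "the value of the non-missing items will be used for the missing item".
- More missing than that in any criterion: "the total CAPS-5 score will be considered missing overall".

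No rounding is stated, and no endpoint is exempted.

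Three endpoints use individual items rather than sums. SAP 9.2.1 lists "Change from baseline in CAPS-5 Reckless or Self-Destructive Behavior (item E-2)" and "Change from baseline in CAPS-5 Sleep Disturbance (item E-6)" for MMRM analysis without multiple imputation. SAP 7.2.4.4.2 defines Loss of Diagnosis as Response plus "no longer meeting DSM-5 symptom criteria required for diagnosis on the CAPS-5 in any one or more of the four clusters". For binary endpoints, SAP 9.2.2 says: "Participants with missing data will be analyzed as though they are non-responders".

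**The concern.** Averaging within a criterion is a reasonable way to complete a sum. It is not a measurement of one particular symptom, and it does not answer whether enough symptoms reach a threshold.

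For E-2 and E-6, a programmer following the text would enter a value that reflects other arousal symptoms and pass it to the MMRM as observed. The MMRM could have handled the missing visit value without it.

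For Loss of Diagnosis, the question is whether a filled item can ever count as a symptom that is still present. If it cannot, an incomplete interview is scored for cluster status as though the unrated symptom were absent. That favours declaring a cluster lost, whereas SAP 9.2.2 resolves missing data against response.

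Elsewhere the SAP does limit such a rule: the SDS adjustment in 7.2.3.2 is written expressly for the total score. The CAPS-5 rule carries no such limit.

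**Working it through.** **Inputs**

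- Items per criterion: B 5, C 2, D 7, E 6 (SAP 7.2.2).
- Item range 0 to 4 (SAP 7.2.4.4.3).
- Symptom criteria: at least one item scored 2 or more in B and in C, at least two in D and in E (Protocol 8.2, inclusion criterion 2). SAP 7.2.4.4.2 does not restate them.
- Response: a fall of at least 10 points in the total (SAP 7.2.4.4.1).

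The plan gives no figure of its own to reproduce.

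**Step 1. Cluster status.** A filled item matters only if the observed items fall short of the criterion. In B and C, falling short means every observed item is at most 1. In D and E, it means at most one observed item is 2 or more, so the highest mean has one item at 4 and the rest at 1.

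| Criterion | Missing | Largest fill when observed items fall short | Score patterns | Status changed by fill |
|---|---|---|---|---|
| B | 1 | 4/4 = 1.0 | 70 | 0 |
| B | 2 | 3/3 = 1.0 | 35 | 0 |
| C | 1 | 1/1 = 1.0 | 5 | 0 |
| D | 1 | (4+5)/6 = 1.5 | 210 | 0 |
| D | 2 | (4+4)/5 = 1.6 | 126 | 0 |
| E | 1 | (4+4)/5 = 1.6 | 126 | 0 |
| E | 2 | (4+3)/4 = 1.75 | 70 | 0 |

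Every fill in the table is below 2. Enumerating all 70+35+5+210+126+126+70 = 642 observed-score patterns, the filled cluster status never differs from the status with the missing items counted as absent. A fill can reach 2 (69 of 126 patterns for E with one item missing), but only where the observed items already meet the criterion.

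**Step 2. Dependence on rounding.** If fills were rounded to the nearest whole number, status would change in 1+1+1+3 = 6 patterns, all in D or E. For example, observed E items 4,1,1,1,1 give 1.6, rounded to 2. If fills were rounded up, it would change in 6+6+6+6 = 24. B and C never change.

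**Step 3. Response.** In the total, the fill adds the criterion mean, not zero. Suppose the baseline total is 40, the true Week 12 total is 30, E-2 is truly 0 but unrated, and the other five E items sum to 11.

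- True change: 30 − 40 = −10, so Response is met.
- Fill: 11/5 = 2.2. Recorded total: 32.2. Recorded change: −7.8, so Response is not met.

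If another cluster is truly lost, this participant is wrongly denied Loss of Diagnosis.

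**Step 4. Single items.** With E-6 unrated, other E items of 0,0,0,1,1 record E-6 as 2/5 = 0.4, and 3,3,3,3,3 record it as 3.0, whatever the sleep symptom was. With E-2 at 0 at baseline and unrated at Week 12, the other items of Step 3 record a worsening of 2.2 points.

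**Step 5. Possible size.** The documents give no item-missing rate, so this step rests on assumptions. A one-factor item simulation (loadings 0.5 to 0.85, Week 12 mean totals 29 to 38, baseline at least 33, one item missing) gave:

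- a false cluster loss in 1.5% to 5.7% of interviews that truly still met all four clusters;
- a false Loss of Diagnosis in 1.0% to 4.4% of those interviews;
- a true Loss of Diagnosis wrongly denied in 0.2% to 1.2% of all interviews.

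If 1% to 5% of 125 Week 12 interviews per arm had one filled item, that is 1.25 to 6.25 interviews. At 4.4%, at most 0.06 to 0.28 participants per arm would be falsely credited.

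**The case against.** The strongest reply is about scope. The rule follows directly on the text about the total and cluster scores, and its only stated consequence is a missing total. A reading limited to sums is natural, and if the sponsor means that, E-2 and E-6 are unaffected. This stands as a reason to call the point a gap in the wording. It does not remove the gap, because the text refers to CAPS-5 items without qualification.

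A reader might infer that every missing item pushes Loss of Diagnosis in the participant's favour. The documents do not support that. The one-way result holds for cluster status with unrounded means, while the Response part can err in either direction. Beyond the fill limits the total is missing, so Response cannot be derived and the participant counts as a non-responder. Nor should cluster-loss rates be read as error rates for the endpoint, which also needs Response.

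A reader might extend the cluster bias to Remission. Meeting all four clusters takes a total of at least 2+2+4+4 = 12, so a total of 10 or less already implies a lost cluster. Remission is exposed only to the fill in the total.

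A reader might see a contradiction with SAP 9.2.2. Completing items first and then treating participants without a score as non-responders is a coherent order. The two rules lean in different directions but do not conflict.

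A reader might also treat E-2 as a safety measure at risk. It is not among the safety endpoints in SAP 2.2.3, and suicidal and self-injurious behavior is captured by the C-SSRS (SAP 10.3).

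**Conclusion.** The concern holds in limited form. As written, the rule gives E-2 and E-6 a value that does not measure them. It also makes cluster status in Loss of Diagnosis equivalent to scoring unrated items as absent, provided means are not rounded. The error in Loss of Diagnosis itself is not strictly one-way; in the illustrative simulation it leaned towards crediting the endpoint.

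The practical effect is probably small. The rule is a fallback after site queries and is the same in both arms. The affected endpoints are outside the fixed testing sequence, with p-values that SAP 7.1.1.1 calls descriptive. The ceiling of 2+1+2+2 = 7 filled items out of 20 is arithmetic, not an expectation. Without an item-missing rate, the effect on the arm comparison cannot be computed. The suitability of averaging for the primary CAPS-5 total is not in question here.

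**What to change.** 1. In SAP 7.2.2, state that within-criterion averaging applies only to criterion sub-scores and the CAPS-5 total. When E-2 or E-6 is not rated, treat that endpoint as missing at that visit and leave it to the MMRM.
2. In SAP 7.2.4.4.2, derive cluster status from observed items. Where missing items leave a cluster undetermined, do not credit Loss of Diagnosis on that cluster, in line with the non-responder rule in 9.2.2. Rounding then no longer matters for cluster status.

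The second change is a conservative choice that statisticians could debate. It would, for example, withhold credit on Criterion B when four items are rated 0 and the fifth is unrated, so some true losses of diagnosis may be denied. A sensitivity count with missing items scored as absent would show how much depends on it.

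The cost is a few sentences in the SAP before unblinding and minor programming. No new data are needed, and the primary and key secondary analyses do not change.

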### 7.2.3 Key Secondary Efficacy Assessments

#### 7.2.3.1 Clinician Global Impression – Severity (CGI-S)

The CGI-S will be completed by an Investigator to evaluate the patient's severity at the time of the assessment. The CGI-S status is a key secondary efficacy endpoint in this study. The CGI-S should be completed toward the end of each in-clinic study visit (except Screening), once all of the assessments are available for the investigator's review. An Investigator will complete the CGI-S assessment at Baseline, Week 4, 8 and 12 (Visits 2, 4, 5 and 6, respectively) in order to assess the overall patient severity status, and answer the following question:

Considering your total clinical experience with this particular population, how mentally ill is the patient at this time?

- 1 = Normal, not ill at all
- 2 = Borderline mentally ill
- 3 = Mildly ill
- 4 = Moderately ill
- 5 = Markedly ill
- 6 = Severely ill
- 7 = Among the most extremely ill patients

The key secondary analysis of CGI-S will treat it as a continuous variable (scored 1-7 as above).

#### 7.2.3.2 Sheehan Disability Scale (SDS)

The SDS scale is a self-report questionnaire that was designed to assess the participant's view of the degree to which symptoms have disrupted work/school, social life/leisure activities, and family life/home responsibilities during the previous two weeks ([Sheehan & Sheehan, 2008](#)). In addition, the SDS asks the participant to provide the number of days of work/school lost as well as unproductive days in the past two weeks. The SDS scale will be completed by the participant at Baseline and after 4, 8, and 12 weeks of treatment (Visits 4, 5, and 6, respectively). A total score will be calculated summing the three individual 11-point (0-10) scales. For participants that do not respond to the work/school disruption because the participant checked the box indicating he/she has not

worked or attended school for reasons unrelated to the disorder (PTSD), the total score will sum the other two domain questions and multiply by 1.5 (rounding up to the nearest whole number) to maintain the scale of 0-30 for the total score. Participants with missing values on the other items will be missing for the total.

#### 7.2.3.3 PROMIS Sleep Disturbance Instrument

PROMIS refers to the Patient-Reported Outcome Measurement Information System ([www.nihpromis.org](http://www.nihpromis.org)), a National Institutes of Health (NIH)-funded initiative to develop instruments to be used across chronic conditions.

The PROMIS sleep disturbance scale (short form 8a) will be assessed at Baseline and after 4, 8, and 12 weeks of treatment (Visits 4, 5, and 6, respectively).

The sleep disturbance scale will be calculated summing the individual item scores of the 8 items. These summed scores will be transformed to T-scores using the published conversions (see [Section 14.2](#)).

### 7.2.4 Other Efficacy Outcomes

#### 7.2.4.1 Clinician Global Impression of Improvement (CGI-I)

The CGI-I will be completed by an Investigator to evaluate the participant's status since initiation of treatment. The CGI-I, status since initiation of treatment, is a secondary efficacy endpoint in this study. The CGI-I should be completed toward the end of each in-clinic post-Baseline study visit once all other assessments are available for the investigator's review. Once the participant has been randomized, an Investigator completes the CGI-I assessment after 4, 8, and 12 weeks of treatment in order to assess the overall change in the participant's status and answer the following question:

Since the initiation of treatment at Visit 2, the participant is:

- 1 = Very much improved
- 2 = Much improved
- 3 = Minimally improved
- 4 = No change
- 5 = Minimally worse
- 6 = Much worse
- 7 = Very much worse

The secondary analysis of CGI-I will treat it as a continuous variable (scored 1-7 as above). There will be an additional secondary responder analysis presented where a responder on the CGI-I is defined as a participant who is scored as 'Very much improved' or 'Much improved' and compared between the study arms.

#### 7.2.4.2 Patient Global Impression of Change (PGIC)

The PGIC is a validated, self-report instrument to gauge the participant's assessment of change in condition. This form will be completed by the participant after 4, 8, and 12 weeks of treatment (Visits 4, 5, and 6, respectively). The participant will answer a single question:

Since the initiation of study medication, my PTSD symptoms are:

- 1 = Very much improved
- 2 = Much improved
- 3 = Minimally improved
- 4 = No change
- 5 = Minimally worse
- 6 = Much worse
- 7 = Very much worse

A responder on the PGIC is a participant who scores himself as ‘Very much improved’ or ‘Much improved.’

#### 7.2.4.3 Montgomery-Åsberg Depression Rating Scale (MADRS)

The MADRS is a validated, 10-item, clinician-administered depression scale that has been used in clinical research since 1979 ([Montgomery & Åsberg, 1979](#)). The MADRS scale will be completed at Screening (Visit 1), Baseline (Visit 2) and after 4, 8 and 12 weeks of treatment (Visits 4, 5 and 6, respectively). The 10 items measure the core symptoms and cognitive features of clinical depression. This scale has historically been used in drug-treatment trials due to its particular sensitivity to detect treatment effects. Since there is a comparative lack of emphasis on somatic symptoms, the scale is useful for the assessment of depression in subjects with physical illness (as may be the case in subjects with PTSD).

#### 7.2.4.4 CAPS-5 Additional Endpoint Definitions

##### 7.2.4.4.1 Response

Response is defined as  $\geq 10$ -point improvement from baseline in CAPS-5 total score.

##### 7.2.4.4.2 Loss of Diagnosis

Loss of Diagnosis at any time point is defined as Response AND no longer meeting DSM-5 symptom criteria required for diagnosis on the CAPS-5 in any one or more of the four clusters (B, C, D, E).

##### 7.2.4.4.3 Sustained Remission

Remission at any time point is defined as a Loss of Diagnosis and a CAPS-5 total score of  $\leq 10$ . Remission that is sustained is defined by meeting remission criteria after both 8 AND 12 weeks of treatment.

A CAPS-5 total score of  $\leq 10$  was selected for remission based on [name] (National Center for PTSD) communication that empirical data suggested the CAPS-5 score range from 0 to 10 was “asymptomatic/few symptoms”. In large multicenter pharmacotherapy trials of PTSD that utilized the prior 17-item CAPS for DSM-IV, remission was defined as achieving a score of  $< 20$  ([Krystal et al, 2011](#)) or  $\leq 20$  ([Davidson et al, 2006](#)). Direct mathematical extrapolation of a score of 20 on prior CAPS version, considering the different scaling for intensity/frequency (0-4 on CAPS-5; 0-8 on CAPS for DSM-IV), would be ((remission score of 20/17-items CAPS for DSM-IV)/2

(scaling))\*20-items CAPS-5) = 11.8 or about 12. Although <12 or  $\leq 12$  were considered as more comparable with these definitions from studies using the prior version of CAPS, the definition of  $\leq 10$  was ultimately chosen as the more stringent approach.

